7.4.1. Key Secondary Efficacy Endpoints with Alpha-Protection

For testing whether relugolix + E2/NETA (Group A) is statistically significantly superior to placebo (Group C) for the primary efficacy endpoint as well as the seven key secondary endpoints listed below, a gate-keeping mixed sequence testing procedure will be applied to maintain the family-wise type I error rate. Under this testing procedure, the primary endpoint

Statistical Analysis Plan

[figure not shown]
Amendment 1: Effective June 14, 2019

MVT-601-3001 and 3002

[figure not shown]
will be tested first at a 2-sided 0.05 significance level. If the p-value for primary endpoint is < 0.05 , the seven key endpoints listed below will be tested sequentially in the order depicted in [Figure 3 \(LIBERTY 1\)](#) and [Figure 4 \(LIBERTY 2\)](#).

For the relugolix + E2/NETA group to be considered statistically superior to the placebo group on a secondary endpoint, the two-sided p-value must be < 0.05 for that secondary endpoint and for all higher-ranking secondary endpoints, as well as for the primary endpoint. If the two-sided p-value is < 0.05 for the fourth endpoint (proportion of women with hemoglobin ≤ 10.5 g/dL at Baseline who achieve an increase of > 2 g/dL from Baseline at Week 24 for LIBERTY 1; proportion of women who achieve a maximum NRS score ≤ 1 for uterine fibroid-associated pain over the last 35 days of treatment in the subset of women with a maximum pain score ≥ 4 during the 35 days prior to randomization for LIBERTY2), the remaining three endpoints (the fifth, sixth, or seventh) will be tested using the Hochberg step-up procedure.

Figure 3: Mixed Sequence Testing Procedure for Primary and Key Secondary Endpoints in LIBERTY 1

Abbreviations: BPD = Bleeding and Pelvic Discomfort; EP = endpoint; Hgb = hemoglobin; max = maximum; MBL = menstrual blood loss; M-vol = myoma volume; NRS = Numerical Rating Scale; PE = primary endpoint; Prop = proportion; UFS-QoL BPD = Uterine Fibroid Symptom and Health-Related Quality of Life Bleeding and Pelvic Discomfort; U-vol = uterine volume.

Figure 4: Mixed Sequence Testing Procedure for Primary and Key Secondary Endpoints in LIBERTY 2

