Abbreviations: BPD = Bleeding and Pelvic Discomfort; EP = endpoint; Hgb = hemoglobin; max = maximum; MBL = menstrual blood loss; M-vol = myoma volume; NRS = Numerical Rating Scale; PE = primary endpoint; Prop = proportion; UFS-QoL BPD = Uterine Fibroid Symptom and Health-Related Quality of Life Bleeding and Pelvic Discomfort; U-vol = uterine volume.

From the Hochberg procedure, the p-values will be calculated for the three endpoints (5, 6, and 7) and ranked from the smallest to the largest. The endpoint corresponding to the largest p-value gets tested first. If the p-value is < 0.05 , then no further testing will occur, and it will be concluded that all three endpoints are positive. Otherwise, the endpoint corresponding to the second largest p-value will be tested. If the p-value is < 0.025 , then no further testing will occur, and it will be concluded that the endpoints corresponding to the middle and smallest p-values are positive. Otherwise, the endpoint with the smallest p-value will be tested. If the p-value is < 0.0167 , no further testing will occur, and it will be concluded that only the endpoint with the smallest p-value is positive. Otherwise, all three endpoints did not pass the statistical significance criterion at 0.05 level.

The seven key secondary efficacy endpoints are as follows:

1. Proportion of women who achieve amenorrhea over the last 35 days of treatment;
2. Percent change from Baseline to Week 24 in MBL volume;

- 3. *Change from Baseline to Week 24 in Bleeding and Pelvic Discomfort Scale score as measured by the UFS-QoL Symptom Severity Scale (Q1, Q2, Q5);*
- 4. *Proportion of women with a hemoglobin ≤ 10.5 g/dL at Baseline who achieve an increase of > 2 g/dL from Baseline at Week 24*
- 5. *Proportion of women who achieve a maximum NRS score ≤ 1 for uterine fibroid associated pain over the last 35 days of treatment in the subset of women with a maximum pain score ≥ 4 during the 35 days prior to randomization;*
- 6. Percent change from Baseline to Week 24 in uterine fibroid volume;
- 7. Percent change from Baseline to Week 24 in uterine volume.

For key secondary efficacy endpoints (1, 4, and 5) that are evaluating proportions, treatment comparisons will be performed using a stratified Cochran-Mantel-Haenszel test with the randomization stratification factors as strata. Point estimates and 2-sided 95% CIs for treatment differences in proportions will be provided.

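### Section 7.4.1 does not name the Hochberg set by study (by list number it contradicts the LIBERTY 2 gate), and its rule on higher-ranking endpoints contradicts the Hochberg step in both studies

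*SAP*

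**What the plan says.** All of this is in SAP Section 7.4.1, Amendment 1.

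- **Order.** The primary endpoint "will be tested first at a 2-sided 0.05 significance level". If it succeeds, "the seven key endpoints listed below will be tested sequentially in the order depicted in" Figure 3 for LIBERTY 1 and Figure 4 for LIBERTY 2.
- **General rule.** A claim of superiority is subject to this condition: "the two-sided p-value must be < 0.05 for that secondary endpoint and for all higher-ranking secondary endpoints, as well as for the primary endpoint". No endpoint is exempted.
- **Gate.** The Hochberg step opens if p < 0.05 "for the fourth endpoint (proportion of women with hemoglobin ≤ 10.5 g/dL at Baseline" and so on, in LIBERTY 1. For LIBERTY 2 the same parenthesis names the pain endpoint and ends "during the 35 days prior to randomization for LIBERTY2), the remaining three endpoints", which go to Hochberg as fifth, sixth and seventh.
- **Hochberg step.** "the p-values will be calculated for the three endpoints (5, 6, and 7) and ranked from the smallest to the largest". The thresholds are 0.05, 0.025 and 0.0167, and the text allows for only the endpoint with the smallest p-value being positive.
- **List.** One numbered list serves both studies. Item 4 is "Proportion of women with a hemoglobin ≤ 10.5 g/dL at Baseline who achieve an increase of > 2 g/dL from Baseline at Week 24", item 5 is pain, and items 6 and 7 are fibroid volume and uterine volume.
- **Use of the numbers.** After the list, the section assigns methods by list number (1, 4 and 5 for proportions; 6 and 7 for ANCOVA; 2 and 3 for the repeated-measures model). It calls hemoglobin key secondary endpoint 4 and pain key secondary endpoint 5, with no distinction between studies.

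**The concern.** This section is the confirmatory decision rule for label claims, so it should lead any two statisticians to the same set of positive endpoints. It falls short in two places.

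First, the numbers 5, 6 and 7 can be taken as ranks or as list labels. In LIBERTY 1 the two coincide. In LIBERTY 2 they do not, because pain is fourth in the sequence but number 5 in the list. A programmer who takes the labels, as the rest of the section does, builds a Hochberg set containing the endpoint that has just served as the gate and lacking hemoglobin.

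Second, the general rule demands significance on every higher-ranked secondary endpoint. Hochberg does not use rank among the last three. Applied as written, the general rule would withdraw a positive result that the Hochberg paragraph grants. This affects both studies and does not depend on how the first ambiguity is settled.

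**Working it through.** **1. Thresholds.** With alpha = 0.05 two-sided and three endpoints, Hochberg uses 0.05/1 = 0.05, 0.05/2 = 0.025 and 0.05/3 = 0.0167. These match the SAP.

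**2. The two readings in LIBERTY 2.** Assume ranks 1 to 3 are as in the list.

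| Reading of 5, 6, 7 | Hochberg set in LIBERTY 2 | Agrees with the gate rule? |
|---|---|---|
| Rank | hemoglobin, fibroid volume, uterine volume | Yes: these are the three left after pain |
| List label | pain, fibroid volume, uterine volume | No: pain is already used, hemoglobin is absent |

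**3. Illustration for LIBERTY 2.** Suppose the primary and first three secondary endpoints pass, with pain p = 0.03, hemoglobin 0.001, fibroid volume 0.20 and uterine volume 0.30. The gate passes (0.03 < 0.05).

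- By rank: 0.30 ≥ 0.05; 0.20 ≥ 0.025; 0.001 < 0.0167. Hemoglobin is positive and pain stays positive.
- By label: 0.30 ≥ 0.05; 0.20 ≥ 0.025; 0.03 ≥ 0.0167. Nothing passes. Pain is positive at the gate but not in Hochberg, and hemoglobin has no test.

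**4. Illustration of the higher-ranking rule, LIBERTY 1.** Suppose everything through hemoglobin passes, with pain p = 0.20, fibroid volume 0.30 and uterine volume 0.001.

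- Hochberg: 0.30 ≥ 0.05; 0.20 ≥ 0.025; 0.001 < 0.0167. Uterine volume is positive.
- General rule: pain (0.20) and fibroid volume (0.30) rank higher in the list and both exceed 0.05. Uterine volume is not superior.

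**5. Error rates.** The LIBERTY 2 tail was simulated with 400,000 runs per scenario. The assumptions are not from the SAP: all earlier tests passed, normal z-statistics with common correlation 0 or 0.5, 80% power taken as a mean z of 2.8, and a strong pain effect as a mean z of 10.

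| Quantity | Correlation 0 | Correlation 0.5 |
|---|---|---|
| Family-wise error, pain strong, other three null: rank reading | 0.0491 | 0.0454 |
| Same: label reading | 0.0500 | 0.0482 |
| Same: label reading plus hemoglobin tested at 0.05 outside Hochberg | 0.0976 | 0.0885 |
| Hemoglobin rejected, pain strong, other three at 80% power: rank reading | 0.764 | 0.752 |
| Same: label reading | 0 | 0 |
| Pain passes its gate but fails the retest, all four at 80% power: label reading | 0.0354 | 0.048 |

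The independent case can be checked by hand.

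- Label reading, pain p near 0: a false rejection of a volume needs both p-values below 0.05, or one below 0.025 with the other at 0.05 or more. That is 0.05² + 2 × 0.025 × 0.95 = 0.0025 + 0.0475 = 0.05.
- Adding a separate hemoglobin test at 0.05: 1 − 0.95 × 0.95 = 0.0975.
- Rank reading, three nulls: 0.05³ + 3 × 0.025² × 0.95 + 3 × (0.05/3) × (0.975² − 0.025²) = 0.0001 + 0.0018 + 0.0475 = 0.0494.

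**6. The higher-ranking rule and alpha.** That rule adds a condition for success. Imposing it on top of Hochberg can only remove rejections, so it cannot raise type I error.

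**The case against.** The strongest reply is that the intent is plain. The order is delegated to Figures 3 and 4, and all seven endpoints are said to be tested. Pain, once tested as the gate, cannot be among the endpoints left over. The numbers in the Hochberg paragraph come before the list and can be read as echoing the ordinals of the gate rule. Table 1 and Appendix 1 both list hemoglobin as alpha-protected with no exception for LIBERTY 2. The abbreviation note to Figure 4 includes hemoglobin, which suggests that the diagram shows it, although the diagram itself could not be read in the text used here.

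Most of this stands. It establishes that the rank reading is the intended one. It does not remove the conflict for someone working from the Hochberg paragraph and the list, because the section otherwise uses those numbers as labels. The SAP version before Amendment 1 carries the same Hochberg sentence with a single order for both studies, where rank and label agreed, so the phrase appears to have been carried over unchanged.

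On the second point, the reply is that the general rule describes the sequential part of a mixed procedure and that the detailed Hochberg text governs the last three. That is a sensible reading, but the sentence does not limit itself to the first four, and the two give opposite answers in the LIBERTY 1 illustration.

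**Conclusion.** The concern holds as a contradiction in wording, in two places. In LIBERTY 2 the Hochberg set, read by list number, conflicts with the gate rule. In both studies the unrestricted rule on higher-ranking endpoints conflicts with the Hochberg step. Each can change which endpoints are declared positive, as the two illustrations show. Their p-values are chosen for illustration.

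Two stronger readings are tempting and are not supported.

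- A reader might infer that the plan leaves hemoglobin untested in LIBERTY 2. The gate rule, Table 1, Appendix 1 and the note to Figure 4 all point to its inclusion; it drops out only on the label reading.
- A reader might infer that type I error is inflated. On the label reading alone it stays near 5% (0.048 to 0.050 in the simulated scenarios). About 9 to 10% arises only if hemoglobin is also tested at 0.05 outside Hochberg, with pain effective and the other three null. Section 7.4.1 provides for no such test. Appendix 1 does show a flat 0.05 criterion for every key secondary endpoint, but as a summary table it does not replace the gated procedure.

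The practical cost of the label reading is therefore a lost hemoglobin test and possible conflicting results for pain (3.5% to 4.8% of runs with all four endpoints at 80% power), under the assumptions stated. The point is worth correcting because this is the confirmatory rule; it does not undermine the design.

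**What to change.** Make two edits to Section 7.4.1.

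1. In the Hochberg paragraph, replace the numbers 5, 6 and 7 with named sets, checked against Figures 3 and 4. LIBERTY 1: gate hemoglobin, Hochberg set pain, fibroid volume and uterine volume. LIBERTY 2: gate pain, Hochberg set hemoglobin, fibroid volume and uterine volume.
2. Limit the higher-ranking sentence to the first four secondary endpoints, and state that the last three follow Hochberg alone once the primary and the first four have passed.

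The cost is SAP wording only. Thresholds, sample size and data collection are unchanged. The edit belongs before unblinding, with the analysis programs for each study checked against the named sets.

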4.3.4. Definition of Baseline Value and Post-Baseline Value

Unless otherwise specified, Baseline values are defined as the last measurement before the first administration (date and time) of study drug. A post-Baseline value is defined as a measurement taken after the first administration of study drug. Change from Baseline is defined as (post-Baseline value – Baseline value). Both date and time of study drug administration and measurement will be considered when calculating Baseline value. If the time is not available, then the date alone will be used. For patients who receive no study medication, the date of randomization will be used in place of the date of first dose in determining Baseline and post-Baseline values.

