a maximum pain score ≥ 4 during the 35 days prior to randomization without restricting number of days of pain scores recorded in the e-Diary.

The analysis for endpoint 5 (proportion of women who achieve a maximum NRS score ≤ 1 for uterine fibroid-associated pain over the last 35 days of treatment in the subset of women with a maximum pain score ≥ 4 during the 35 days prior to randomization) will also be performed using NRS scores reported on eDiary during menstrual and non-menstrual days.

For key secondary efficacy endpoints (6 and 7) evaluating percent change from Baseline in uterine fibroid volume and uterine volume that are measured only at Week 24, an analysis of covariance (ANCOVA) model will be used to assess treatment effect with treatment, randomization stratification factors and Baseline value as covariates.

For key secondary efficacy endpoints (2 and 3) evaluating the change (absolute or % change) from Baseline to Week 24, treatment comparisons will be performed using a mixed model repeated measures approach with treatment, visit, randomization stratification factors and treatment by visit interactions included as fixed effects and random effects (from the individual patients). In this model, an unstructured variance-covariance matrix is assumed for each patient.

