7.4.2. Other Secondary Efficacy and Exploratory Endpoints

The following describes the analysis methods for other secondary efficacy endpoints and exploratory endpoints. There are three types of analyses corresponding to the three types of endpoints (time-to-event, continuous and binary) (see [Appendix 1](#) for details).

Time-to-Event Endpoint

For time to achieving an MBL volume of < 80 mL AND at least a 50% reduction from Baseline MBL volume (as an event), time to event will be defined as weeks from date of first dose of study drug to response (event) based on the MBL volume as assessed by the alkaline hematin method. The missing data handling rules described in Section [7.3.5](#) for deriving responder status at Week 24/EOT will be applied similarly at Weeks 8, 12, 16, and 20. Patients without an event will be censored at the last assessment date prior to the last dose of the study drug.

Kaplan-Meier methods will be used to describe the time to event distributions. A log-rank test stratified by the randomization stratification factors using the proportional hazard model (p-value from score test) will be used to compare relugolix + E2/NETA to placebo. Randomization stratification factors will be used to stratify inferential testing.

Continuous Endpoints

For endpoints evaluating the change (absolute or percent change) from Baseline to Week 24, treatment comparisons will be performed using a mixed model repeated measures approach with treatment, randomization stratification factors, visit, and treatment by visit interactions included as fixed effects. The Baseline value will be included as a covariate, and an unstructured variance-covariance matrix will be assumed. Calculation of the dependent variable (change from Baseline) for each patient at each visit will be calculated based on the visit windows specified in Section [4.3.5](#). Based on this model, the least squares mean at Week 24 will be compared between treatment groups and summarized along with the corresponding 95% CIs for treatment difference. In addition, summary statistics (mean change or mean % change) will be graphically presented as appropriate.

Binary Endpoints

For endpoints evaluating proportions, treatment comparisons will be performed using a stratified Cochran-Mantel-Haenszel test as appropriate with the randomization stratification factors as strata. Point estimates and 2-sided 95% CIs for treatment differences in proportions will be provided.

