Change from Baseline to Week 24 in the UFS-QoL Symptom Severity Scale score	mITT	Mixed-effects model	P < 0.05	Week 12, 24	LS means for change
Change from Baseline to Week 24 in the UFS-HRQL total score	mITT	Mixed-effects model	P < 0.05	Week 12, 24	LS means for change
Change in PGA for uterine fibroid related function from Baseline to Week 24	mITT	Mixed-effects model	P < 0.05	Monthly	LS means for absolute and change
Change in PGA for uterine fibroid symptoms from Baseline to Week 24	mITT	Mixed-effects model	P < 0.05	Monthly	LS means for absolute and change
Proportion of patients achieving improvement in PGA for uterine fibroid symptoms from Baseline to Week 24	mITT	Cochran-Mantel-Haenszel test	P < 0.05	Monthly	Frequency and percentages
Proportion of patients achieving improvement in PGA for uterine fibroid related function from Baseline to Week 24	mITT	Cochran-Mantel-Haenszel test	P < 0.05	Monthly	Frequency and percentages
Safety Related Endpoints					
% Change from Baseline to Week 12 in BMD (pooled data)	Safety population	Mixed-effects model Relugolix Group A vs B	P < 0.05	Week 12	LS means Diff (95%CI)

Secondary Endpoints	Analysis Population	Statistical Method/Test	Declare Statistical Significance ^a	Time Points of Summary	Summary Statistics
% Change from Baseline in BMD	Safety population	Mixed-effects model Relugolix Group A vs Placebo at 12/24 weeks; Relugolix Group B vs Placebo at 12 weeks		Week 12, 24	LS means Diff (95%CI)
Exploratory Secondary Efficacy Endpoints					
Change from Baseline to Week 24 in the Menorrhagia Impact Questionnaire Score for physical activities	mITT	Descriptive		Monthly	Frequency and percentages
Change from Baseline to Week 24 in the Menorrhagia Impact Questionnaire Score for social and leisure activities	mITT	Descriptive		Monthly	Frequency and percentages

Abbreviations: KM, Kaplan-Meier; LS, least squares; mITT, modified intent-to-treat; NRS, Numerical Rating Scale; Q, question; UFS-HRQL, Uterine Fibroid Scale – Health-related Quality of Life.

^a P-values are two-sided.

APPENDIX 2. DERIVATION AND PSYCHOMETRIC EVALUATION OF A UFS-QOL BLEEDING AND PELVIC DISCOMFORT SCALE

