3.3.2. Scale Level Analysis of the BPD Scale

3.3.2.1. Internal Consistency

Internal consistency was assessed for the BPD Scale at Baseline and Week 12. Reliability was acceptable at Baseline (> 0.70) and good at Week 12 (> 0.80 ; [Table 3.3-2](#)).

Table 3.3-2: Cronbach's Alpha Coefficient of BPD Scale by VISIT (MVT-601-3001 and 3002)

n		Q1	Q2	Q3	Alpha ^a
		Mean (SD)	Mean (SD)	Mean (SD)	
Baseline	260	3.97 (0.95)	3.85 (1.09)	3.59 (1.18)	0.768
Week 12	258	2.75 (1.47)	2.69 (1.46)	2.64 (1.36)	0.882

Abbreviations: n, number of patients; Q, question; SD, standard deviation.

^a Cronbach Coefficient Alpha

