3.3.2.5. Ability to Detect Change

The BPD Scale's ability to detect change was assessed through the difference in BPD Scale scores over time in patients who have changed with respect to the measurement concept as measured by the PGA (symptoms). For each PGA stratified group, within person change from Baseline to Week 12 and standardized effect size statistics (SES) for change over the same period were assessed. SES statistics judged were based on Cohen's recommendations (small change, 0.20; moderate change, 0.50; large change, 0.80).

Results showed that the mean change for improving PGA categories had a monotonically increasing pattern from patients who had a PGA change of 0 to patients who had a PGA improvement of -4 (Table 3.3-6). Worsening groups (PGA change of +1 or +2) had very low levels of mean change, with wide standard deviations around the mean due to the low sample size in these categories.

In line with expectations, the SES statistics for the improvement categories (PGA score change of -1 to -4) were large (> 0.80) compared to the moderate SES found in the patients who reported no change (PGA score change of 0; SES = 0.55).

Table 3.3-5: Summary Statistics of BPD Scale Score at Baseline by PGA (symptoms) Response (MVT-601-3001 and 3002)

Baseline PGA	Baseline BPD Scale Score ^a						
	N	Mean	SD	Median	Q1, Q3	Min	Max
1	7	53.57	28.81	58.33	25.00, 75.00	16.67	91.67
2	21	59.92	26.56	58.33	41.67, 75.00	8.33	100.00
3	96	62.33	21.18	66.67	41.67, 75.00	8.33	100.00
4	89	75.09	19.48	75.00	66.67, 91.67	16.67	100.00
5	47	83.51	16.53	91.67	75.00, 100.00	41.67	100.00

Abbreviations: BPD, bleeding and pelvic discomfort; max, maximum; min, minimum; N, number of patients; PGA, Patient Global Assessment; Q1, first quartile; Q3, third quartile; SD, standard deviation.

a Transformed Score.

Table 3.3-6: Summary Statistics of Change from Baseline BPD Scale Score to Week 12 by PGA (symptoms) Change from Baseline (MVT-601-3001 and 3002)

PGA Change Category ^a	N	Mean	SD	95% CI	Median	Q1, Q3	Min	Max	Effect Size ^b
-4	23	-48.19	(42.27)	(-66.47, -29.91)	-66.67	-83.33, 0.00	-100.00	25.00	-2.93
-3	50	-49.33	(33.16)	(-58.76, -39.91)	-54.17	-75.00, -25.00	-100.00	33.33	-2.41
-2	74	-27.70	(30.75)	(-34.83, -20.58)	-25.00	-41.67, 0.00	-91.67	25.00	-1.25
-1	48	-23.09	(28.57)	(-31.39, -14.79)	-16.67	-33.33, -8.33	-100.00	33.33	-1.01
0	39	-10.68	(20.32)	(-17.27, -4.10)	-8.33	-25.00, 0.00	-66.67	33.33	-0.55
1	14	1.79	(19.11)	(-9.25, 12.82)	-4.17	-16.67, 8.33	-16.67	33.33	0.07

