4.3.2. Improvement on BPD Scale by PGA Change Category

Uncollapsed changes on the PGA were used to determine minimal meaningful improvement on the BPD Scale (Table 4.3-1). Improvement on the BPD Scale increased monotonically for all the categories from “no change (0)” to “1-category improvement (-1)” to “2-category improvement (-2)” to “3 category improvement (-3)” with nonoverlapping 95% CIs for mean change of the groups. Table 4.3-1 shows further that a 1-category improvement (-1) is associated with a 27.31-point mean improvement in the BPD Scale score at Week 24 compared with Baseline, with a 95% CI [-35.42, -19.19], a large SES = -1.21, and a median improvement of 25.00 points.

Table 4.3-1: Summary of Change from Baseline to Week 24 in UFS-QoL BPD Scale by PGA for Symptom Severity Change Category (mITT Population)

PGA Change Category	N = 255	Change in BPD					Correlation between PGA Change and BPD Change ^a
		Mean (SD)	Median	95% CI	p-value ^b	SES ^c	
4-Category deterioration (+4)	0						0.57
3-Category deterioration (+3)	2	-12.50 (5.89)	-12.5	-65.44, 40.44	0.2048	-2.12	
2-Category deterioration (+2)	2	0.00 (11.79)	0	-105.89, 105.88	1.00	0.0	
1-Category deterioration (+1)	21	-10.32 (16.22)	-8.33	-17.70, -2.93	0.0086	-0.54	
0-Category deterioration (0)	47	-9.93 (23.09)	-8.33	-16.71, -3.15	0.005	-0.42	
1-Category improvement (-1)	47	-27.31 (27.62)	-25.00	-35.42, -19.19	< 0.0001	-1.21	
2-Category improvement (-2)	68	-42.16 (25.71)	-41.67	-48.38, -35.93	< 0.0001	-1.93	
3-Category improvement (-3)	45	-61.85 (26.62)	-66.67	-69.85, -53.85	< 0.0001	-3.25	
4-Category improvement (-4)	23	-54.35 (32.65)	-66.67	-68.47, -40.23	< 0.0001	-4.12	

Abbreviations: BPD = bleeding and pelvic discomfort; CI = confidence interval; mITT = modified intent-to-treat; PGA = patient global assessment; SD = standard deviation; SES = standardized effect size.

mITT is used to calculate change from Baseline score at Week 24 and includes patients from the mITT population who have available change from Baseline data at Week 24.

^a Polyserial correlation coefficient between change in BPD Scale and change in PGA of symptom severity.

^b The p-value for each individual change group is derived from a paired (within-sample) t-test assessing the difference over time.

^c SES is calculated as the mean divided by the SD of Baseline. SES is judged as small = 0.2, moderate = 0.5, and large = 0.8 (Cohen 1988).

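### The repeated-measures model for alpha-protected endpoint 3 (change in BPD score) omits Baseline BPD, which the SAP includes for comparable endpoints; the test is valid but gives up precision for nothing

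*SAP*

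**What the plan says.** Section 7.4.1 gives one repeated-measures model for key secondary endpoints 2 (percent change in MBL volume) and 3 (change in BPD score). Its fixed effects are "treatment, visit, randomization stratification factors and treatment by visit interactions included as fixed effects", with patient random effects and an unstructured covariance matrix. No Baseline value is named.

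Baseline is named elsewhere:

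- For endpoints 6 and 7, section 7.4.1 specifies ANCOVA with "treatment, randomization stratification factors and Baseline value as covariates".
- For the other continuous change endpoints, section 7.4.2 states: "The Baseline value will be included as a covariate, and an unstructured variance-covariance matrix will be assumed". Appendix 1 lists among these "Change from Baseline to Week 24 in the UFS-QoL Symptom Severity Scale score". BPD is items 1, 2 and 5 of that eight-item scale.

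Appendix 1 says only that endpoint 3 uses a mixed-effects model, so the covariate is not supplied there. The stratification factors are region and screening MBL volume; neither is a BPD measure. Section 4.3.4 fixes the outcome: "Change from Baseline is defined as (post-Baseline value – Baseline value".

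**The concern.** The SAP adjusts an unprotected parent scale for its Baseline but not the alpha-protected subscale taken from it, and gives no reason.

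Baseline BPD does enter through the outcome, because change is follow-up minus Baseline. That forces its coefficient to 1. If the true slope of follow-up on Baseline is well below 1, the change score over-corrects. Residual variance is then larger than necessary, and part of any chance imbalance in Baseline BPD stays in the treatment estimate through regression to the mean. The random effects and unstructured covariance describe correlation among post-Baseline changes and do not replace the covariate.

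At stake are efficiency and consistency for a confirmatory endpoint. There is also a procedural risk: if the omission is a drafting slip and is corrected after unblinding, an alpha-protected analysis will have been changed with results known.

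**Working it through.** **Design inputs.** Section 2.2.1 gives 130 per arm and about 20% dropout, so 130 × 0.8 = 104 evaluable. For the primary endpoint (25% vs 55%, two-sided 0.05), 104 per arm gives 99.5% power, matching the stated at least 99%. The SAP states no effect or power for endpoint 3.

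**Week 12, from the SAP's blinded pooled tables.** The table titled "Alpha Coefficient of BPD Scale by VISIT (MVT-601-3001 and 3002" (Table 3.3-2) gives item SDs and Cronbach's alpha. Its third column is headed Q3, but the mean of 3.59 matches Q5 in Table 3.3-1: (21 + 48 + 171 + 384 + 310)/260 = 3.59. For three items, total variance = sum of item variances/(1 − 2α/3), and the 0–100 scale multiplies the SD by 100/12.

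- Baseline: (0.95² + 1.09² + 1.18²)/(1 − 0.512) = 3.483/0.488 = 7.137; SD = 2.672 × 8.333 = 22.26. The groups in Table 3.3-5 pool to 22.25.
- Week 12: (1.47² + 1.46² + 1.36²)/(1 − 0.588) = 6.142/0.412 = 14.91; SD = 3.861 × 8.333 = 32.18.
- Change: the table titled "Summary Statistics of Change from Baseline BPD Scale Score to Week 12 by PGA (symptoms) Change from Baseline" (Table 3.3-6, n = 254) pools by variance = [Σ(n−1)SD² + Σn(mean − grand mean)²]/(N − 1) = (225,379 + 61,658)/253; SD = 33.68.
- Covariance = (22.26² + 32.18² − 33.68²)/2 = 198.4.
- Slope = 198.4/22.26² = 0.40; correlation = 198.4/(22.26 × 32.18) = 0.28.
- Variance removed by adjustment = (1 − 0.40)² × 22.26²/33.68² = 0.157, about 16% (SE down about 8%).

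**Week 24.** The table titled "Summary of Change from Baseline to Week 24 in UFS-QoL BPD Scale by PGA for Symptom Severity Change Category" (Table 4.3-1, n = 255) pools to (163,971 + 93,108)/254, so change SD = 31.81. Baseline SD = 17.38/0.790 = 22.0 (Table 4.3-2, pooled effect size). The Week 24 score SD, W, is not given, so it is assumed:

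slope = (22.0² + W² − 31.81²)/(2 × 22.0²); variance cut = (1 − slope)² × 22.0²/31.81²

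| Assumed W | Slope | Variance cut |
|---|---|---|
| 24 | 0.05 | 43% |
| 28 | 0.27 | 26% |
| 30.2 (slope as at Week 12) | 0.40 | 17% |
| 32 | 0.51 | 11% |
| 34 | 0.65 | 6% |
| 36 | 0.79 | 2% |

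**Chance imbalance.** One SE of the Baseline difference is 22.0 × √(2/104) = 3.05 points. The part left in the estimate is 3.05 × (1 − slope): 1.8 points at slope 0.40, and 1.1 to 2.2 points for W = 34 to 28.

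**Power.** Two-sample t-test, two-sided 0.05, 104 per arm, SD = 31.81 × √(1 − cut), as an approximation to the repeated-measures model. The true differences are assumptions.

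| True difference | Unadjusted | Adjusted, W = 34 | Adjusted, slope 0.40 | Adjusted, W = 28 |
|---|---|---|---|---|
| 12 | 77.3% | 79.7% | 84.5% | 88.2% |
| 15 | 92.3% | 93.7% | 96.1% | 97.6% |
| 20 | 99.5% | 99.6% | 99.9% | 99.9% |

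The pooled SD includes between-arm differences. Removing d² × 2/9 from both variances (1:1:1, active arms assumed equal) gives 79% to 81–90% at 12 points and 93% to 95–98% at 15. With that within-arm SD and all 130 per arm, the figures are 87% to 89–95% and 97% to 98–99%.

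**Type I error.** In 5,000 simulated trials per setting (104 per arm, one final visit, slopes 0.4 and 0.6), the unadjusted test rejected in 5.0% to 5.1% and the adjusted test in 5.3%.

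**The case against.** The strongest reply is that nothing here is wrong. A pre-specified change-score model with stratification factors is a legitimate analysis. Sections 7.4.1 and 7.4.2 cover different endpoint sets, and endpoints 6 and 7 use a different model because they are measured only at Week 24. The sentence serves endpoints 2 and 3 together and repeats the terms of the imputation model in section 7.3.6, so it looks like a shared model rather than a slip over BPD. All of that stands as a description. But the rationale in 7.3.6 concerns percent change in MBL volume and does not carry over to BPD. Endpoint 2 at least has the Baseline MBL stratum as a partial proxy for its own Baseline; endpoint 3 has none of its own.

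The size is also open to challenge. The Week 24 slope cannot be derived from the SAP. The Week 12 slope comes from slightly different samples (n = 260, 258, 254) among early patients who completed Week 24 assessments. The MBL stratum may already absorb some Baseline BPD, since two of the three items concern bleeding and clots; any overlap would shrink the gain. The 12- and 15-point differences are the reviewer's assumptions. At 17.38 points (an anchor-group contrast in Table 4.3-2, not a planned treatment effect), unadjusted power with 104 per arm is already 97.5%, against about 99% with a 17% cut. These points limit the gain but do not give a reason to forgo it.

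**Conclusion.** The concern holds as a matter of efficiency and consistency, and should be fixed. It is not an error in the test: the comparison is unbiased under randomization and keeps its level. With dropout, validity also requires that missingness not depend on Baseline BPD beyond what the model and the observed changes carry; including Baseline would relax that requirement.

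The omission is certain from the text. The size is less so. The Week 12 cut of about 16% in residual variance follows from the SAP's own tables, pooled over three blinded arms and ignoring overlap with the strata. The Week 24 cut of 6% to 26% rests on an assumed score SD of 34 down to 28. The loss is modest if the true BPD difference is 12 to 15 points and negligible at 20 or more. BPD's place in the test order is in figures not available here, so nothing is claimed about lower-ranked endpoints.

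**What to change.** Before unblinding, add the continuous Baseline BPD score, optionally with a Baseline-by-visit term, to the fixed effects for endpoint 3 in section 7.4.1, in line with section 7.4.2. Since endpoint 2 shares the sentence, state explicitly which terms apply to each endpoint.

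The cost is one sentence and one degree of freedom (one per visit with the interaction). The score is already collected, and every change score already requires it, so no patient drops out of the analysis.
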